**CONFIDENTIAL**

minimizing the use of concentrated solutions and selecting large veins for infusion of solutions.

- *Arginine*: Overdosage, especially in children, can be fatal. To reduce this risk, the dose of arginine will be weight based (0.07 gm/kg in children) with a maximum dose of 5 gm per dose in both adults and children.

## ***7.5 Potential Benefits***

There is potential benefit of participation by individuals with either prediabetes or type 2 diabetes. Prediabetic participants are at increased risk of developing diabetes and may benefit from the frequent monitoring and testing that will allow earlier recognition should their condition progress; treatment is also predicted to slow progression from prediabetes to type 2 diabetes. Participants with type 2 diabetes will benefit through the close monitoring and the improvement in glucose control that should occur in all subjects. In addition, they have the potential to receive insulin or liraglutide that should further improve glucose control in them and potentially slow progression of their disease. Further, liraglutide could help with weight loss. As all subjects have a condition that is becoming more prevalent and carries with it the risk of additional complications, participation will also benefit the individual, the researchers and society through the gaining of new knowledge.

## ***7.6 HIPAA – Protection of Patient Information***

All data collected in the process of pre-screening, screening, and conducting the proposed research will be stored and maintained locally and centrally in compliance with HIPAA regulations. Access to study data will be secure with limited, password-protected access. Only study personnel who are IRB approved will have access to data collected as part of these studies. Data entered into the central database will be stored at the CoC on a server that is maintained with the highest stringency of protection. Similarly, data entered into local databases will be stored at the clinical center on a server that is maintained with the highest stringency of protection.

## **8 ADVERSE EVENT REPORTING**

An adverse event is defined as any medical problem experienced by a RISE participant whether or not considered intervention-related by the clinical center staff. The timely and complete reporting of adverse events is a critical requirement in the conduct of this trial. In 2013 the FDA issued an IND exemption for the RISE Study. Therefore, the study group and NIDDK are not required to report any study adverse events to the FDA.

**CONFIDENTIAL**

### ***8.1 Definition of Serious Adverse Events***

- a. The event results in an inpatient hospitalization (any overnight stay associated with an admission).
- b. The event results in the prolongation of a hospital stay.
- c. The event results in permanent or severe disability.
- d. The event results in death.
- e. A pregnancy results in a congenital anomaly.
- f. The event results from an overdose (either accidental or experimental) of the study medication.
- g. The event is life-threatening.
- h. Treatment is required to prevent a serious event.

### ***8.2 Non-serious Adverse Events***

Non-serious adverse events are all AEs which do not meet the above criteria for “serious”.

### ***8.3 Reporting Adverse Events***

AEs will be ascertained in an unbiased manner using standard questions that are identical and identically administered to participants in all treatment arms. To accomplish this, AEs will be reported on a standard form that is completed by the study staff at each regular study visit following commencement of study-related activities. Targeted non-serious AEs (e.g., abdominal pain) are ascertained by asking questions relating to specific events of import in prediabetic or diabetic participants as well as side effects that may be associated with any of the study treatment arms. AEs also include any significantly abnormal laboratory result obtained on the patient between visits or at the time of the visit.

The clinical center staff who learn of an SAE must data enter the completed RISE Serious Adverse Event Report prior to the close of the following business day. Upon request, all SAEs will be reported within the prescribed period to the relevant pharmaceutical sponsors.

All pregnancies occurring during the study must be reported by the clinical center staff to the CoC. This reporting must occur prior to the close of the business day that follows the clinical center becoming aware of the pregnancy. Further, the outcome of the pregnancy must be determined and reported by clinical center staff as soon as possible after the pregnancy is completed. All this information will be reported within the prescribed period to the relevant pharmaceutical sponsors.

**CONFIDENTIAL**

## 8.4 Tracking Adverse Events

- *Serious Adverse Events:* SAEs will be monitored by the RISE Safety Monitoring Committee, which will remain blinded to treatment arm. The external DSMB will monitor SAEs by treatment arm. It is important to note that all serious and unexpected AEs must be reported to the CoC, regardless of the drug-related assessment. For example, a patient struck by lightning requires a report, even though this is not likely to be a drug related event.
- *Non-serious adverse events:* Non-serious AEs are tabulated by the CoC in periodic reports. Summaries of the AEs, tabulated by clinic, are provided to the Safety Monitoring Committee, which reviews this summary during one of its regularly scheduled meetings.
- *Safety Monitoring Committee:* The Safety Monitoring Committee reviews AEs in a blinded fashion. The committee considers whether changes in the protocol (monitoring, consent process, etc.) are indicated based on the occurrence, frequency, or severity of AEs. The committee also evaluates whether there is any clustering of AEs by clinic. Any concerns on the part of the Safety Monitoring Committee may be referred to the Safety Review Officer and/or DSMB, which can review SAEs in an unmasked manner.
- *Safety Review Officer:* The Safety Review Officer will review any SAEs where the SMC is not in agreement about whether the event is related to study drug, as well as certain specified SAEs of concern (e.g., pancreatitis). The Safety Review Officer will not be blinded and will confirm or reject the causality determination of the SAE to study intervention. As deemed necessary, he/she may contact the local site PI to obtain additional information about the SAE. Any concerns on the part of the Safety Review Officer may be referred to the DSMB.

## 8.5 Emergency Unmasking

The Safety Monitoring Committee remains blinded to treatment group. If a SAE warrants unblinding, an on-call member of the Safety Monitoring Committee is available for consultation at all times. Unblinding will be performed by a selected member of the study group in combination with the CoC.

# 9 STATISTICAL CONSIDERATIONS

All analyses will be conducted under the intention-to-treat principle using the treatment as assigned to each participant, and using all available data from all participants. Analyses of study data will be conducted to address the primary and secondary objectives of the trial, other stated objectives, and other interrelationships among elements of study data of interest to the investigators and of relevance to the objectives of the study.

**CONFIDENTIAL**

## ***9.1 Primary Outcome and Analyses***

Two primary outcomes each measuring  $\beta$ -cell function after 3-months of washout will be assessed for this trial. In order to maintain a study-wide  $\alpha=0.05$ , a closed testing procedure will be used to assess the primary outcome [89]. The closed testing procedure is a method of hierarchical testing which tests higher-order comparisons before allowing lower-level comparisons, thus controlling the type I error and preserving power. First,  $\beta$ -cell function will be compared across the four treatment groups using an analysis of covariance model adjusted for baseline  $\beta$ -cell function. From this model, the overall test of equality across the four treatment groups will be computed. If that overall test is significant at the  $\alpha=0.05$  level, then each of the four possible sets of three interventions will be compared in four separate analysis of covariance models. The final significance testing of any set of two treatment groups is only undertaken if the p-values for each of the two 3-intervention tests which include a particular two intervention group are both  $p<0.05$ . For example, for interventions  $I_1$ ,  $I_2$ ,  $I_3$  and  $I_4$ , the first analysis of variance test  $I_{1234}$  assesses whether there are any differences among the four groups. If the overall test across the four groups is not significant, testing concludes and no treatment group is declared different from any other. Alternately, if that initial 4-group test is significant at the  $\alpha=0.05$  level, four separate analysis of covariance models with combinations  $I_{123}$ ,  $I_{124}$ ,  $I_{134}$  and  $I_{234}$  are tested. The comparison  $I_{12}$  is only tested if both  $I_{123}$  and  $I_{124}$  are significant at  $p<0.05$  and so forth. The closed testing procedure is chosen as the primary outcome analysis to maintain an overall study-wide  $\alpha=0.05$  while preserving power and allowing each set of interventions to be compared under pre-specified circumstances. The two primary outcomes will be analyzed separately with a total type I error probability of 0.05 for each, i.e. without an adjustment for two separate outcomes.

Each ANCOVA model will employ White's robust (information sandwich) estimate of the covariance matrix of the model coefficients as the basis for inference [90]. This approach preserves power and protects the type 1 error probability when the homoscedastic normal errors assumptions are violated.

## ***9.2 Secondary Outcomes and Analyses***

Comparisons of the primary study outcomes will be made for those with vs. without diabetes at study entry, by race/ethnicity and sex, by baseline HbA1c and  $\beta$ -cell function, and by categorical groups of various biomarkers.

Analysis of covariance will be used to compare the three intervention groups and the placebo group for the primary measures of  $\beta$ -cell function at the end of the active intervention phase (12-months) and 9-months post-washout as well as for additional continuous variables of

**CONFIDENTIAL**

interest at the end of the intervention phase (12-months) and at 3-months and 9-months post-washout. As for the primary outcomes, all analyses will be adjusted for the baseline value of each outcome and will use the closed testing procedure described above to preserve an overall  $\alpha=0.05$  for those outcomes as well.

An important secondary analysis of this study is to determine whether  $\beta$ - and  $\alpha$ -cell function from OGTT and fasting samples are sufficiently well correlated with more robust assessments of  $\beta$ - and  $\alpha$ -cell function obtained from the hyperglycemic clamp to validate their use in large clinical trials. For these analyses, Pearson and non-parametric Spearman correlations of simple versus sophisticated measures of  $\beta$ - and  $\alpha$ -cell function will be computed. Correlations will be assessed for measures made both on and off therapy.

Finally, to examine biomarker associations with glucose metabolism, Pearson and non-parametric Spearman correlations of each biomarker with  $\beta$ - and  $\alpha$ -cell function, insulin sensitivity and glucose tolerance measures will be determined. In addition, multiple linear regression models will be developed to predict measures of glucose metabolism with the most informative biomarker sets.

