### ***1.1 Specific Aims and Objectives***

The primary objective of the RISE Adult Medication Study is to compare in a preliminary proof-of-principle trial the efficacy of three treatment strategies versus placebo on measures of  $\beta$ -cell function after 3-months of post-treatment washout that will follow 12-months of active treatment. Participants will have prediabetes or untreated, recent-onset type 2 diabetes, defined by elevations in 2-hour post-challenge glucose levels along with elevations in hemoglobin A1c and/or fasting glucose concentrations. The hypothesis is that, in participants with prediabetes or recent-onset type 2 diabetes, one or more of the strategies aimed at lowering glucose will lead to preservation or recovery of islet function that will be sustained after withdrawal of treatment. To address this hypothesis, we have identified the following primary and secondary specific aims.

The primary specific aim is to determine whether:

- Functional improvements in  $\beta$ -cell function following 12 months of active treatment with (1) metformin alone for 12 months, (2) insulin glargine short term (3 months) followed by metformin for 9 months, or (3) the combination of liraglutide plus metformin for 12 months can be maintained for at least 3 months following the withdrawal of therapy, compared to placebo.

The secondary specific aims are to determine in this same cohort whether:

- Treatment with the intervention therapies for 12 months improves  $\beta$ -cell function compared to placebo,
- Functional improvements in  $\beta$ -cell function are maintained for 9 months following the withdrawal of therapy, compared to placebo,

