### **3.3 Secondary Outcomes**

There are a number of pre-specified secondary outcomes. These include measures derived from the hyperglycemic clamp that are not specified as primary outcomes; measures derived from the OGTT; analyses related to treatment effect at the end of the 12 month active intervention period compared to pre-treatment baseline; and analyses related to various putative predictors of treatment outcome.

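### Section 9.2 credits the closed test with an overall 0.05 error rate for the secondary outcomes, but the procedure covers only arm comparisons for one outcome at one visit

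*Protocol*

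**What the plan says.** Protocol section 9.1 defines the procedure. A four-arm ANCOVA comes first. If it is significant at 0.05, "each of the four possible sets of three interventions will be compared in four separate analysis of covariance models". A pair of arms is tested only if both three-arm sets that contain it are significant. The stated purpose is strong: "The closed testing procedure is chosen as the primary outcome analysis to maintain an overall study-wide" alpha of 0.05. The section then says that the two co-primary outcomes are analysed separately, "with a total type I error probability of 0.05 for each, i.e. without an adjustment for two separate outcomes".

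Section 9.2 carries the procedure over to the secondary outcomes. It plans ANCOVAs of the primary measures at the end of treatment and later, and of further continuous variables of "interest at the end of the intervention phase (12-months) and at 3-months and 9-months post-washout". All of these "will use the closed testing procedure described above to preserve an overall" alpha of 0.05.

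Section 3.3 introduces the family with "There are a number of pre-specified secondary outcomes", and sections 3.3.1 to 3.3.5 list them. They give no order, no key-secondary set and no exploratory label. The SAP is a plan for the primary outcome only and has no multiplicity rule for secondary outcomes.

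**The concern.** A closed test protects only against errors among the hypotheses inside its closure. Here those hypotheses are equalities among treatment arms for a single variable at a single visit. Nothing in 9.1 links one outcome to another, one visit to another, or a secondary test to the primary result. Each outcome-by-visit combination therefore starts afresh at 0.05, and the sentence in 9.2 claims a property that the procedure lacks.

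This matters because the secondary aims in section 1.1 are framed as questions the trial will settle ("The secondary specific aims are to determine in this same cohort whether"). They include benefit at 12 months and persistence 9 months after withdrawal. Section 1.2 says the study should inform whether these approaches go on to larger trials. A reader who relies on 9.2 could treat any significant secondary contrast as error-controlled and give it too much weight in that choice.

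**Working it through.** **Inputs.**
- Four arms (section 1.2); 56 per arm at the end of washout (9.3); each test at 0.05 (9.1).
- Visits for secondary variables: Months 12, 15 and 21 (9.2). The clamp is done at baseline, Month 12 and Month 15, not at Month 21 (6.1.3 and Table 2).
- Number of outcomes: the protocol gives no total. Counting each listed item once, without funding-contingent, duplicate or baseline-only items: 3.3.1 has 5 clamp, 7 OGTT and 4 fasting; 3.3.3 has 6; 3.3.4 has 2; 3.3.5 has 5. Total 5 + 7 + 4 + 6 + 2 + 5 = 29. The two primary measures at Month 12 are added.
- Correlation between tests: not in the documents. Assumed equal for all pairs of tests, at 0, 0.5 and 0.9.

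**Step 1. Reproduce the plan's figure.** One outcome, one visit, all arms equal. The four-arm test has size 0.05 by construction. Simulation with 56 per arm (200,000 runs) gave 0.0496 for the four-arm test and 0.048 for any pairwise claim. So 0.05 is right for one outcome at one visit when no arm differs.

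**Step 2. One outcome, three visits.** For independent tests, the chance that at least one four-arm test rejects is 1 − 0.95³ = 0.143. The simulated chance of at least one false pairwise claim is 0.140 at correlation 0, 0.12 at 0.5 and 0.084 at 0.9. At 0.9 the four-arm test itself gives 0.086.

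**Step 3. The listed family.**
- About 30 outcomes at one visit, independent: 1 − 0.95³⁰ = 0.785.
- Outcome-by-visit tests on the actual schedule: clamp 5 × 2 = 10; OGTT 7 × 3 = 21; fasting 4 × 3 = 12; insulin sensitivity (1 × 2) + (2 × 3) + (3 × 3) = 17; biomarkers 2 × 3 = 6; physical 5 × 3 = 15; primary measures at Month 12, 2 × 1 = 2. Total 83. Independent: 1 − 0.95⁸³ = 0.986.

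Chance of at least one false pairwise claim with no treatment effect, from simulation of the procedure in 9.1:

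| Tests | Correlation 0 | 0.5 | 0.9 |
|---|---|---|---|
| 1 outcome, 1 visit | 0.05 | – | – |
| 1 outcome, 3 visits | 0.14 | 0.12 | 0.08 |
| About 30 outcomes, 1 visit | 0.77 to 0.78 | 0.51 | 0.18 |
| About 83 outcome-by-visit tests | 0.98 to 0.99 | 0.72 to 0.73 | 0.23 |

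**Step 4. Within one outcome at one visit.** A full closure over four arms also contains the joint hypotheses of two disjoint pairs, for example I1 = I2 together with I3 = I4. Section 9.1 omits these. Suppose both equalities are true but the two pairs lie far apart. The four-arm test and all four three-arm tests then almost always reject, and both true pair hypotheses are tested at 0.05. If the two tests are independent, the error is 1 − 0.95² = 0.0975; simulation gives 0.097 to 0.098. A gap of 0.60 SD between the pairs, the effect size in 9.3, already gives about 0.097 with 56 per arm. If only one arm differs from the other three, the error stays near 0.051.

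**The case against.** The strongest reply is that *overall* means over arms, separately for each outcome. Section 9.2 ties its sentence to the primary outcomes, and 9.1 says openly that those get 0.05 each with no adjustment across the two. This reading is fair, and the phrase *study-wide* in 9.1, which points the other way, is qualified by that same statement. But it does not rescue the sentence. Per outcome, a variable tested at three visits still exceeds 0.05 (step 2). Per outcome and visit, the omitted disjoint-pair hypothesis still allows nearly 0.10 (step 4).

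Other parts of the reply stand and limit the point:
- A reader might infer that the false-positive rate is about 50%. That needs about 30 tests at a correlation of 0.5, or 13 to 14 independent tests (1 − 0.95¹³ = 0.487; 1 − 0.95¹⁴ = 0.512). The documents support neither choice. Several listed items are near-duplicates, such as the three fasting insulin-sensitivity indices, or weight and BMI, so one common correlation is a simplification.
- Section 9.2 refers to variables of interest, not to every item in 3.3. Testing the whole list is an assumption.
- A complete absence of effect is a calibration case. It is unlikely for on-drug glucose or weight at Month 12.
- A reader might extend the claim to the subgroup analyses ("Comparisons of the primary study outcomes will be made for those with vs. without diabetes at study entry, by race/ethnicity and sex"). That sentence makes no statement about alpha, so the point does not cover it.
- The trial is called a preliminary proof of principle, and no text says that secondary p-values will be presented as confirmatory. This softens the consequence. But the label covers the primary analysis too, for which error control is claimed, so it does not serve as an exploratory label for the secondary outcomes.
- The SAP's silence follows from its scope, and a separate secondary plan cannot be ruled out.

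**Conclusion.** The point holds as a claim in 9.2 that the procedure does not deliver. Across outcomes and visits there is no control. On the narrower per-outcome reading, one variable at three visits carries about 0.08 to 0.14 instead of 0.05. For the listed family the range is about 0.18 to 0.78 at one visit and about 0.23 to 0.99 over the schedule. The ranges rest on assumed equal correlations from 0.9 to 0, no treatment effect, and every listed item being tested. No single figure within them is established, but every case run with more than one test lies above 0.05. Separately, error for one outcome at one visit can reach about 0.098 when two disjoint pairs of arms differ widely from each other.

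The sentence should be corrected because it is inaccurate and cheap to change. The point does not show that any secondary result will be misreported.

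**What to change.** Replace the sentence in 9.2 with: *The closed procedure addresses comparisons among arms separately for each outcome and time point; it does not control type I error across secondary outcomes or time points.* Report the secondary between-arm comparisons as exploratory estimates with 95% confidence intervals.

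Do not promise strict 0.05 control within one outcome unless the disjoint-pair hypotheses are added to the closure. There are three: I1 = I2 with I3 = I4, I1 = I3 with I2 = I4, and I1 = I4 with I2 = I3.

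An optional alternative is a short ordered list of key secondary outcomes, each with a named visit, tested only after a significant primary result, with everything else labelled exploratory.

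The cost is a few sentences in the protocol or a secondary analysis plan, with no new data or participants. The downside is that secondary p-values can no longer be presented as error-controlled.

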**CONFIDENTIAL**

- Treatment with the intervention therapies for 12 months improves  $\alpha$ -cell function compared to placebo, and whether this improvement is maintained after withdrawal of therapy,
- Measures of  $\beta$ - and  $\alpha$ -cell function from an oral glucose tolerance test (OGTT) and fasting samples made on and off therapy are sufficiently well correlated with more robust and technically demanding assessments, validating use of the simpler measures in large clinical trials, and
- Biomarkers obtained at baseline can predict parameters of  $\beta$ - and  $\alpha$ -cell function, insulin sensitivity and glucose tolerance and the response to an intervention.

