### ***2.8.2 Oral Tests of $\beta$ - and $\alpha$ -cell Function and Insulin Sensitivity***

The OGTT provides measures of islet function and has been used in large clinical trials for this purpose. The early insulin response (insulinogenic index) is an important determinant of glucose tolerance [18]. This response, when used in combination with a fasting measure of insulin sensitivity (1/fasting insulin, HOMA, or QUICKI) provides another estimate of  $\beta$ -cell function termed the “oral disposition index” (DIO) [22, 72]. However, the accuracy of HOMA in assessing changes in insulin sensitivity over time may not be as reproducible and accurate as clamp techniques [73]. Using modeling approaches such as those developed by Mari et al. [74] and Cobelli et al. [75], it is possible to obtain a number of additional parameters of  $\beta$ -cell function and insulin sensitivity from the OGTT. In addition, using C-peptide levels and deconvolution techniques, insulin secretion rates can be calculated from the OGTT [74-76]. Finally, overall glucose tolerance can be calculated from the glucose excursion during the test [77], providing a measure that is directly interpretable and applicable in the clinical setting.

Physiological glucagon suppression during an OGTT is an important determinant of glucose tolerance and provides an estimate of  $\alpha$ -cell function. In individuals with type 2 diabetes, glucagon suppression is impaired [2, 28, 29], an abnormality that is improved with incretin-based therapy [10]. However, whether this change persists after withdrawal of therapy is unknown.

These OGTT-based measures will be performed in the study and their relationship with intravenous test-based measurements will be determined, both at baseline and following drug interventions.

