**CONFIDENTIAL**

## 6 DATA COLLECTION

### 6.1 Main Study Procedures

The timing of major study procedures during the different phases of the study is illustrated in Figure 1. Outcomes using hyperglycemic clamp procedures will be obtained at baseline, at the end of 12 months of treatment, and after a 3-month washout period (i.e., 15 months post randomization). Additional outcomes will be obtained from the OGTT concurrent with the hyperglycemic clamp procedures, and also at additional time points -- at 6 months on therapy, and at 9 months after stopping therapy (i.e., 21 months post randomization). Blood and urine samples for planned measures will be collected at these visits, along with extra blood and urine samples that will be stored for future analyses. Further details on these measures are provided below, and are summarized in Figure 1 above. All procedures and measures will be conducted by centrally trained and certified staff.

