### **9.3 Sample Size/Power Calculations**

There is little preliminary data on the expected differences in the primary outcomes in previously drug-naïve patients following a washout. Several unpublished analyses provided ranges of possible differences between treated and placebo patients, as well as expected correlations between baseline and follow up measures. Therefore, sample size was based on a minimum effect size (i.e., absolute difference between any two groups divided by the standard deviation (SD)) using a two-sided significance level of  $\alpha=0.05$ , and a conservative correlation of 0.57 between baseline and follow up measures. A sample size of 56 per arm (224 total) at the end of the washout provides  $\geq 80\%$  power to detect a minimum effect size of 0.60 between any two treatment groups in either of the primary outcome measurements (see Table 3) for the closed-testing procedure as described above using a baseline-adjusted analysis of covariance. A higher effect size will result in significantly increased power. A total of 255 participants will be recruited to allow for a 10% loss to follow-up over the course of the study.

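### Correlating OGTT and clamp values cannot by itself show that OGTT or fasting measures follow treatment change; Section 9.2 should add change and treatment-effect comparisons

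*Protocol*

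**What the plan says.** Protocol Section 1.1 sets the aim: to determine whether OGTT and fasting measures of β- and α-cell function "are sufficiently well correlated with more robust and technically demanding assessments, validating use of the simpler measures in large clinical trials". Section 9.2 repeats it, calls the analysis important, and gives the method as "Pearson and non-parametric Spearman correlations of simple versus sophisticated measures of" β- and α-cell function. It adds: "Correlations will be assessed for measures made both on and off therapy". Section 2.8.2 describes the same comparison as made "both at baseline and following drug interventions".

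No section names a correlation of changes, a comparison of OGTT with clamp treatment effects as a test of validity, a rule for pooling or separating arms, or a cut-off for an adequate correlation. The SAP covers only the primary outcome.

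Two other provisions matter. Section 6.1 says "Additional outcomes will be obtained from the OGTT concurrent with the hyperglycemic clamp procedures", and Table 2 shows both tests at baseline, Month 12 and Month 15. Section 9.2 also plans baseline-adjusted ANCOVA by arm for additional continuous variables of "interest at the end of the intervention phase (12-months) and at 3-months and 9-months post-washout". The OGTT and fasting measures are listed secondary outcomes in Section 3.3.1.

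**The concern.** An endpoint for a large trial has to register what treatment does. A correlation of two values taken at the same visit answers a different question: whether people who are high on one test are high on the other. Much of that ordering is a stable personal characteristic. Repeating the correlation on and off therapy gives further snapshots; it does not ask whether the two measures move together within a person or show the same treatment effect.

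The protocol itself gives reasons to keep the questions apart. Section 2.8.2 cautions that HOMA may be less accurate than clamp methods for change in insulin sensitivity. Section 2.7 says liraglutide may slow gastric emptying, a route open to an oral test and not to an intravenous one. Section 2.8 notes that the OGTT response includes incretin effects.

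At stake is a conclusion that a simpler measure is fit for larger trials when its responsiveness has not been examined. The point also bears on this trial: Table 2 shows an OGTT but no clamp at Month 21, so the 9-month durability aim has to be read through the OGTT.

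**Working it through.** The documents give no figure for the OGTT–clamp correlation, so there is none to reproduce. What can be checked is whether the reading of the Section 9.3 inputs is right, and then whether a measure with no treatment response could pass the planned check.

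**Inputs from the documents (Section 9.3 and Table 3).** "a conservative correlation of 0.57 between baseline and follow up measures"; adjusted effect size 0.60; two-sided α 0.05; 56 per arm, 224 in total.

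**Step 1: the plan's own figures.** The raw effect is the adjusted effect × √(1 − r²):
- 0.62 × √(1 − 0.60²) = 0.496
- 0.60 × √(1 − 0.57²) = 0.493
- 0.57 × √(1 − 0.50²) = 0.494

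All three rows of Table 3 therefore describe a raw effect of about 0.49 to 0.50 SD. Simulating the closed test (200,000 runs, one arm differing from three equal arms) gives power of 85.8%, 83.0% and 78.2%, against the stated 84%, 81% and 77%. The inputs are being read as intended.

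**Step 2: a measure built to ignore treatment.** These are assumptions, not facts from the documents.
- Clamp value = stable trait T (variance 0.57) + occasion-specific state (variance 0.43). Total variance is 1 and the baseline-to-follow-up correlation is 0.57.
- One arm of four has a clamp effect of 0.493 at follow-up.
- OGTT value = T + its own noise (variance v), with no treatment effect. Values tried for v: 0.05, 0.20, 0.43.

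**Step 3: the planned correlation.** At baseline r = 0.57 / √(0.57 + v):
- v = 0.05: 0.57/√0.62 = 0.72
- v = 0.20: 0.57/√0.77 = 0.65
- v = 0.43: 0.57/√1.00 = 0.57
- ceiling as v approaches 0: √0.57 = 0.755

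At Month 15 the treated arm adds 0.25 × 0.75 × 0.493² = 0.046 to the clamp variance, so each value is divided by √1.046 = 1.023.

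**Step 4: the analyses the plan does not use for validation.** The OGTT change contains only OGTT noise, and the clamp change only clamp state and treatment effect. Their covariance is zero.

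Means over 2,000 simulated trials of 224 participants per setting:

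| | v = 0.05 | v = 0.20 | v = 0.43 |
|---|---|---|---|
| Pearson, baseline | 0.72 | 0.65 | 0.57 |
| Pearson, Month 15 | 0.71 | 0.63 | 0.56 |
| Spearman, Month 15 | 0.69 | 0.61 | 0.54 |
| Correlation of changes | 0.00 | 0.00 | 0.00 |
| Clamp effect significant (pairwise, unadjusted) | 89% | 87% | 88% |
| OGTT effect significant | 5% | 5% | 5% |

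**Step 5: sensitivity.** If the stable share were 0.40 or 0.80 instead of 0.57, the ceiling would be √0.40 = 0.63 or √0.80 = 0.89.

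**The case against.** The strongest reply is that the plan already does much of what is needed. Section 3.3 says secondary outcomes are analysed by intention to treat for effects of randomised treatment, Section 3.3.1 lists the OGTT measures, and Section 9.2 plans ANCOVA by arm. A reader might infer from the validation paragraph alone that OGTT treatment effects are never examined; that is not so. What is missing is any text that brings those estimates to bear on validity.

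A reader might also infer that a poorly responsive measure would be declared valid. The documents do not support that: there is no cut-off and no automatic rule, and Section 1.2 speaks only of information on potential use. Likewise, Section 9.2 does not say that arms will be pooled, so a complaint that pooling inflates the correlations would rest on an assumption. Correlations on and off therapy also give some protection, since they could show the relationship weakening under treatment.

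The illustration has limits. The 0.57 belongs to the primary clamp outcomes across treatment and washout, and nothing in the documents says how the remaining 0.43 divides between real change and measurement error. If it were all independent error, even a perfect surrogate would show a change correlation near zero. A low change correlation is therefore not proof of failure by itself, which is why the treatment-effect comparison is needed beside it.

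Finally, the SAP is by title a primary outcome plan, so its silence proves little. The gap rests on Sections 1.1 and 9.2 of the protocol.

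**Conclusion.** The point holds as one of method. The only statistics tied to the validation aim are correlations of values, and these could look good for a measure that follows neither clamp change nor treatment. Under the stated assumptions such a measure shows correlations of about 0.54 to 0.72, with a change correlation of 0.00 and a treatment effect detected no more often than chance.

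The result shows what the planned statistic could miss. It does not show that any OGTT or fasting measure does fail. The trait/state split and the OGTT noise are assumed; only 0.57, 0.60 and the sample size come from the protocol. This is a secondary aim, and the primary analysis, sample size and power are untouched. The change is worth making because it is cheap and bears directly on the stated purpose.

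**What to change.** In Section 9.2, add two items to the validation analysis:

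- **(a) Change against change.** Estimate the association of OGTT (or fasting-measure) change with clamp change from baseline to Month 12, baseline to Month 15, and Month 12 to Month 15. Adjust for arm and also show it within arm. State that measurement error attenuates change correlations. Give confidence intervals: with 56 per arm, an observed correlation of 0.65 has a 95% interval of 0.47 to 0.78, against 0.57 to 0.72 with 224.
- **(b) Treatment effects side by side.** Tabulate standardised treatment effects with confidence intervals for each OGTT or fasting measure and its named clamp counterpart at Months 12 and 15, taken from the ANCOVAs already planned. Name the pairs in advance, because the SAP models clamp secretion and sensitivity in two equations.

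Keep the Pearson and Spearman correlations as description, and do not base a conclusion about "validating use of the simpler measures in large clinical trials" on them alone.

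The cost is a little more analysis. No new visit, sample or participant is needed.
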